include treatment and Time Block. Trial order will be used as covariate in these analyses to allow evaluation as to whether the order of treatments had a significant effect on the outcome. Appropriate covariance structures will be determined using
covariate in these analyses to allow evaluation as to whether the order of treatments had a significant effect on the outcome. Appropriate covariance structures will be determined using
order of treatments had a significant effect on the outcome. Appropriate covariance structures will be determined using
Appropriate covariance structures will be determined using
Akaikes information criteria to evaluate the best model fit.
Results analysis will be examined for both treatment effects and
the Treatment x Time Block interaction results.
2. Subjects will report Craving measures (AUQ and VAS) collected at 30-minute
lower levels of craving as intervals during the self-administration trials will be used to test
measured by the Visual the effect of pitolisant on alcohol craving. A mixed models
Analog Scale (VAS) and approach will be used to test for differences in craving between
the Alcohol Urge the pitolisant and placebo self-administration trials. Within-
questionnaire (AUQ) subject factors for this analysis will include Treatment and Time
during the pitolisant self- Block. Trial order will be used as covariate in these analyses to
administration trial allow evaluation as to whether the order of treatments has a
compared to the placebo significant effect on the outcome.
self-administration trial.
3. Subjects will BAES scores and BALs obtained during the 40-minute
experience no difference observation period and both of the 60-minute self-administration
in alcohol-induced blocks will be used to test the effect of pitolisant on the
stimulation, as measured stimulating effects of alcohol. A mixed model for repeated
on the BAES, after the measures approach will be used to test for differences between
consumption of the pitolisant and placebo on the stimulant BAES scores at each of
priming dose of alcohol the 10-minute observation intervals and 30-minute self-
when they are receiving administration intervals. This data will be analyzed with
pitolisant as compared to Treatment and Time used as within-subject factors.
when they are receiving
placebo.
5. Subjects will report The alcohol VAS, OCDS, and the TLFB measurements during
lower levels of alcohol the twelve-day period of drug exposure will be used to determine

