For our primary outcomes, separate analyses will be conducted on data collected during the Priming and Self-Administration periods of the test session.

during pitolisant exposure	models repeated measures approach will be used to test for		
period as compared to	differences in craving and consumption between the pitolisant		
placebo exposure period.	and placebo trials. Treatment will be used as within-subject		
	factor. VAS measures taken on each of the twelve days of drug		
	exposure, repeated measures mixed models analysis will be		
	conducted with Day and Treatment as within-subject factors.		
6. Subjects will not report	Daily hours of sleep and number of minutes spent awake during		
significant differences in	the twelve-day period of drug exposure will be used to determine		
the number of hours sleep	the effect of pitolisant on craving and consumption. Mixed		
per night and minutes	Models repeated measures approach will be used to test for		
spent awake during the	differences in sleep quality between the pitolisant and placebo		
pitolisant exposure period	trials. Treatment will be used as within-subject factor. Sleep		
as compared to the	measures taken on each of the twelve days of drug exposure,		
placebo exposure period	repeated measures mixed models analysis will be conducted with		
	Day and Treatment as within-subject factors.		

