### 12.2 Sample Size Determination

A group size of 28 completers was selected for use in this study based on an assumed effect size of 0.7 suggested by similar alcohol self-administration studies with amount consumed as the primary outcome. This effect size is in the range we found for the anticonvulsant zonisamide used in a similar alcohol self-administration study. The sample size for this study is based on an estimated reduction of 1.5 standard drinks with an estimated standard deviation (2.1) of the between Challenge Trial differences in alcohol self-administration, with an effect size of this magnitude (i.e. 0.7). This requires a sample size of 28 to allow for detection of a significant within-subject difference in alcohol consumption with an alpha value of 0.01 and power value of 0.81. Based on an estimated 15-20% rate of non-completion for randomized subjects, we anticipate randomizing 36 subjects to achieve a sample of 28 completers. Given our experience with recruiting AUD populations into clinical trials, we expect a screening exclusion rate of roughly 50%. Approximately 72 subjects will be consented and screened in clinic to yield a sample of 36 eligible subjects. Given that this a laboratory based experiment we do not plan to conduct any planned interim analyses in this study.

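### Hypotheses 3 (alcohol stimulation) and 6 (sleep) claim no difference but are analysed only with tests for a difference, and the contrast that decides Hypothesis 3 is not named

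*Combined protocol and SAP*

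**What the plan says.** Section 4.2.2 lists the stimulant effects of alcohol and sleep quality as secondary outcomes.

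**Hypothesis 3** (section 12.1) is that stimulation on the BAES after the priming dose will not differ between pitolisant and placebo. The data are "BAES scores and BALs obtained during the 40-minute" observation period and both 60-minute self-administration blocks. A mixed-model repeated "measures approach will be used to test for differences between" "pitolisant and placebo on the stimulant BAES scores at each of" the 10-minute and 30-minute intervals. Treatment and Time are the within-subject factors.

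**Hypothesis 6** (section 12.1) begins "6. Subjects will not report" and goes on to say that it is significant differences, in hours slept and minutes awake, that will not be reported. Its mixed model tests for "differences in sleep quality between the pitolisant and placebo" periods.

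Two other statements bear on this:

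- The test session is split by period for primary outcomes only: "For our primary outcomes, separate analyses will be conducted on data collected during the Priming and Self-Administration periods of the test session".
- The only significance level in the plan is in section 12.2, where 28 completers are said to detect a within-subject difference in alcohol consumption "with an alpha value of 0.01 and power value of 0.81".

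**The concern.** A test for a difference can show that an effect exists. When it fails to reject, it does not show that the effect is absent or small. Hypothesis 6 is worded so that a p-value above alpha fulfils it. For Hypothesis 3 that reading is an inference from its wording and from section 3.1; no section states it outright. In both cases noisier data make the predicted outcome more likely, which is the wrong incentive.

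Both outcomes bear on reassurance about the drug. Section 3.1 says it is important to establish that pitolisant does not add to the stimulating effects of alcohol. Section 3.1 also names insomnia and sleep disturbance as possible effects, and section 6.1 reports insomnia in 6% on pitolisant against 2% on placebo.

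A second problem applies to Hypothesis 3 alone. It is about the priming dose, which is the same under both treatments. In the self-administration blocks subjects choose how much to drink (section 9), and Hypothesis 1 predicts that they drink less on pitolisant. If so, block BAES scores compare the treatments at different alcohol exposures. The plan does not say which contrast decides Hypothesis 3 or how BAL enters the model.

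**Working it through.** **Inputs.** From section 12.2: 28 completers; effect size 0.7; alpha 0.01; power 0.81; 36 randomized; "Based on an estimated 15-20% rate of non-completion for randomized subjects". Assumed: one summary contrast per subject, analysed as a paired comparison, and two-sided 0.05 as the level for these outcomes, with 0.01 as the alternative. The documents give no SD for BAES or sleep, so effects are in units of the SD of the within-subject difference.

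**1. The plan's own figure.** For a paired t-test, power = P(|T| > t(1−α/2, n−1)), where T is noncentral t with n−1 degrees of freedom and noncentrality d√n. With d = 0.7, n = 28 and two-sided α = 0.01, the noncentrality is 0.7 × √28 = 3.70, the critical value is 2.77, and power is 0.815. This matches the stated 0.81, so the method agrees with the plan's.

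**2. Completers.** 36 × 0.80 = 28.8 and 36 × 0.85 = 30.6, so 28 and 30 are both shown.

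**3. Chance that a true difference is non-significant.** This is P(|T| < critical value) from the same distribution.

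| True difference (SD) | n = 28, α 0.05 | n = 28, α 0.01 | n = 30, α 0.05 | n = 30, α 0.01 |
|---|---|---|---|---|
| 0.3 | 0.666 | 0.861 | 0.645 | 0.847 |
| 0.4 | 0.468 | 0.722 | 0.437 | 0.695 |
| 0.5 | 0.277 | 0.537 | 0.246 | 0.497 |

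**4. What a non-significant result leaves open.** The 95% CI half-width is t(0.975, n−1)/√n. For n = 28 it is 2.052/5.292 = 0.388 SD; for n = 30 it is 2.045/5.477 = 0.373 SD. At n = 28 the largest estimate that is non-significant at 0.05 is 0.388 SD, and its upper limit is 0.388 + 0.388 = 0.776 SD. This is the boundary case, not a typical result.

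**5. What a margin-based claim could achieve.** Power to exclude harm beyond margin m when the true difference is zero is P(T > t(1−α, n−1)), with noncentrality m√n.

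| Margin (SD) | Power at n = 28, one-sided 0.05 | Completers for 80% | Power at n = 28, one-sided 0.025 | Completers for 80% |
|---|---|---|---|---|
| 0.3 | 0.461 | 71 | 0.334 | 90 |
| 0.4 | 0.662 | 41 | 0.532 | 52 |
| 0.5 | 0.825 | 27 | 0.723 | 34 |

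With a true harm of 0.1 SD, the one-sided 0.05 powers fall to 0.270, 0.461 and 0.662.

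**6. Which contrast decides Hypothesis 3.** The schedule gives about four BAES readings in the observation period (every 10 minutes for 40) and four in the blocks (every 30 minutes for 120). Hypothesis 1 names the terms to be examined: treatment, and treatment by time block. Hypothesis 3 names none. If every interval were tested at 0.05 with no true effect, the chance of at least one false difference under independence would be 1 − 0.95⁴ = 0.19 for four intervals and 1 − 0.95⁸ = 0.34 for eight. The unnamed choice therefore affects the verdict.

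**The case against.** **The 67% is one scenario.** It assumes a single test, whereas Hypothesis 3 refers to each interval and Hypothesis 6 has two sleep outcomes. If any significant component counted against no difference, a real effect would be missed less often. A simulation with 28 completers, two-sided 0.05, the same true difference on every component and assumed correlations of 0.5 to 0.8 gives these chances that all tests are non-significant:

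| Components | True 0.3 SD | True 0.5 SD |
|---|---|---|
| 2 | 51–57% | 14–19% |
| 4 | 36–48% | 6–13% |
| 8 | 23–41% | 2–9% |

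This stands as a limit on the size. The plan fixes neither the decision rule nor the correlations. It does not rescue the inference, because non-significance on several tests is still not evidence of no difference.

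**The question may be whether there is an increase.** Section 3.1 also puts it that way, and a difference test answers it when an increase is found. It does not support the prediction when none is found.

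**The post-priming contrasts can be obtained, and BALs are collected.** True. What is missing is a statement of which contrast decides and how BAL is used. The BAL part is missing detail rather than an error, and no size can be put on the effect of chosen intake.

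**Both outcomes are secondary in a small laboratory study, and mixed models give estimates and intervals anyway.** Also true. Adverse-event calls continue regardless (section 10.2). This keeps the point below the level of the primary analysis and makes the repair cheap.

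**Conclusion.** The concern holds. The plan makes two no-difference predictions and gives only difference tests to judge them, with no margin, interval criterion or alpha. For Hypothesis 6 this follows from its wording; for Hypothesis 3 it is inferred. With 28 completers and a single contrast at two-sided 0.05, a true 0.3 SD difference would pass as no difference in about two of three trials, and a 0.5 SD difference in just over one of four. At 0.01 the figures are 86% and 54%. They rest on the single-contrast assumption and fall if several components are tested and any one can overturn the prediction. They cannot be put in BAES points or minutes of sleep, because no SD is given.

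Hypothesis 3 also lacks a named deciding contrast, and its analysis window is wider than the hypothesis. The sample size and primary tests are not affected. What changes is what the trial may conclude on stimulation and sleep. This should be fixed before unblinding.

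**What to change.** In section 12.1:

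1. State that Hypotheses 3 and 6 will be judged by the estimated pitolisant-minus-placebo difference with its 95% CI, and that non-significance will not be reported as no difference.
2. Decide Hypothesis 3 on BAES stimulation over the 40-minute observation period after the priming dose. Report the self-administration blocks separately, noting that they reflect chosen intake.
3. State whether and how BAL enters the model.
4. Only if the sponsor wants to claim no meaningful increase in stimulation or worsening of sleep: before unblinding, fix a justified margin in scale units and the confidence level, and require the one-sided limit in the harmful direction to lie inside the margin.

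Items 1 to 3 are wording and need no added data. Their price is that a no-difference statement becomes harder to make. Item 4 may be out of reach at the planned size. For a 0.5 SD margin with a true difference of zero, power at 28 completers is about 82% at one-sided 0.05 but 72% at one-sided 0.025, the level that matches a 95% CI. Smaller margins need more completers than planned at either level.

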#### Drug exposure period:

Randomized subjects will receive 12 days of study medication at the time of randomization. A riboflavin tracer (25 mg for 4.45 mg pill; 50 mg for 17.8 mg pill) will be added to each capsule to serve as an objective measure of medication adherence using urine obtained on the day of the alcohol challenge. Two bottles will be dispensed to each subject. One bottle will contain 14 pills of pitolisant (4.45 mg) or placebo and the other bottle will contain 5 pills of pitolisant (17.8 mg) or placebo. All pills will be over-encapsulated with 25 mg (4.45 mg pill) or 50 mg (17.8 mg pill) of riboflavin. Subjects will take an 8.9 mg dose (two 4.45 mg pills) of pitolisant or placebo

once per day on day 1 through 7. Subjects will then take a 17.8 mg dose (one 17.8 mg pill) of pitolisant or placebo once per day on day 8 through 12. The 17.8 mg pill will be overencapsulated with 50 mg of riboflavin. Based on the published half-life for pitolisant, subjects should reach steady state levels after 5 days of taking the 17.8 mg dose. This dosing plan is consistent with the FDA approved prescribing information for the treatment of narcolepsy.

During the twelve-day period of drug exposure, subjects will be asked to answer a medication compliance question each day by smartphone using the REDCap data capture App. In addition to assessing medication compliance, subjects will also be asked to rate their craving for alcohol each day using the alcohol VAS. Subjects will receive a \$5 reimbursement on each day they complete the VAS and answer the medication compliance question using the REDcap smartphone App. Sleep quality during the drug exposure period will also be assessed by having subjects complete items from the National Sleep Foundation Sleep Diary each day. Items to be completed will include daily reports on the total number of hours slept per night and on the number of times and number of minutes for awakening during the night.

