### Medication Visit #2

After the 7-14 day washout period subjects will return to the lab to receive study medication prior to the alcohol challenge #2. Subjects will complete the same tests and interviews completed during the randomization visit (See appendix A for schedule of events). Based on the assessments at medication visit #2, subjects be discontinued for the following reasons: pregnancy, recreational drug use except for marijuana, evidence of non-compliance with study medication, suicidal thoughts or behavior, and use of a new medication that would make participation unsafe. Subjects will receive a 12-day supply of study medication and will be scheduled for the alcohol challenge #2. Subjects will be allowed to delay start of medication for up to 7 days after randomization in order to accommodate scheduling for the alcohol challenge trial.

Alcohol Challenge Trials 1 & 2: Subjects will return to the laboratory on day 12 of drug exposure for each medication trial to complete the alcohol challenge. For safety reasons, subjects will be asked to arrange transportation plans (no driving) prior each of the alcohol challenge trials. There will be a 7-14 day washout period between alcohol challenge Trial 1 and medication visit #2. The washout may extend to 14 days to accommodate the scheduling of the medication visit. Concomitant medications, urine drug screening, urine pregnancy testing, blood alcohol level will be assessed to determine eligibility to proceed with the challenge. Blood alcohol level must be 0.000 to continue with the study procedures. Urine collected for drug screening will be exposed to ultraviolet light as an objective test of medication compliance. If no fluorescence is observed in the urine sample the subject will be excluded from continuing with the challenge. Measures of drinking (TLFB) and cravings (OCDS, VAS and AUQ) will be collected to inform secondary outcomes. Subjects will be observed taking the morning dose of pitolisant (or placebo) on the day of the challenge (after compliance is confirmed via a urine screening). The peak plasma concentration of pitolisant should be reached approximately 60 minutes after administration. The alcohol self-administration session will begin no sooner than one hour after the administration of the observed 17.8 mg morning dose. The alcohol selfadministration will be conducted in the GCRU. The room will be a carpeted and furnished with

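### The daily craving and sleep models (H5, H6) have no day-of-week term, so weekend mismatch between a subject's two 12-day windows adds small but avoidable imprecision

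*Combined protocol and SAP*

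**What the plan says.** Section 12.1 gives the models. Under H5, for the "VAS measures taken on each of the twelve days of drug" exposure, and under H6, for the daily sleep items, the repeated-measures mixed model is "conducted with Day and Treatment as within-subject factors". No weekday, weekend or calendar term is named there or elsewhere. For H5 craving and consumption in general (which includes TLFB and OCDS) the section names only Treatment as a within-subject factor.

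The sleep data are described in section 9 under Drug exposure period: "Items to be completed will include daily reports on the total number of hours slept per night", together with awakenings during the night.

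The length and position of each window come from section 9. The first dose step is taken "once per day on day 1 through 7", and the second step is "pitolisant or placebo once per day on day 8 through 12". The challenge closes the window: "Subjects will return to the laboratory on day 12 of drug exposure for each medication trial". Two scheduling allowances separate the windows: "There will be a 7-14 day washout period between alcohol challenge Trial 1 and medication visit #2", and "Subjects will be allowed to delay start of medication for up to 7 days after randomization". No passage ties the two challenges to the same weekday.

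**The concern.** Twelve days is not a whole number of weeks. Days 1-7 always contain one full week, but the content of days 8-12 depends on the weekday of the first dose. If a subject's two windows start on different weekdays, the pitolisant and placebo periods can contain different numbers of weekend days. If craving or sleep differs between weekends and weekdays, part of that pattern enters the within-subject treatment difference as noise.

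The study Day factor does not remove it. Day 9 may be a Saturday for one subject and a Tuesday for another, so a common Day effect averages over weekdays. It would absorb the pattern only if everyone started on the same weekday.

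What is at stake is precision in two secondary hypotheses for which section 12.2 states no power. H6 deserves most attention, because it predicts no significant difference in sleep, and avoidable noise makes that result easier to obtain.

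**Working it through.** **The plan's own figure.** The documents give no figure for weekends or for H5/H6 power. The only power statement (section 12.2) is 28 completers, effect size 0.7, alpha 0.01, power 0.81. A two-sided paired t-test (noncentral t) gives 0.815, so it reproduces. It concerns laboratory consumption and is not affected here.

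**Step 1: distance between period starts.** Day 12 falls 11 days after day 1. Washout is 7 to 14 days and start delay 0 to 7 days (section 9).

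- Offset = 11 + washout + delay, from 11 + 7 + 0 = 18 to 11 + 14 + 7 = 32 days.
- The weekday is preserved only at 21 or 28 days, that is, washout + delay = 10 (4 ways) or 17 (5 ways).
- This is 9 of 8 x 8 = 64 combinations, or 14%. It shows what the windows allow, not how visits will be booked.

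**Step 2: weekend days per window, by weekday of the first dose.**

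| First dose | Days 1-7, Sat/Sun | Days 8-12, Sat/Sun | Days 8-12, Fri/Sat |
|---|---|---|---|
| Mon | 2 | 0 | 1 |
| Tue | 2 | 1 | 2 |
| Wed | 2 | 2 | 2 |
| Thu | 2 | 2 | 2 |
| Fri | 2 | 2 | 2 |
| Sat | 2 | 2 | 1 |
| Sun | 2 | 1 | 0 |

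Under either definition the 12-day total is 2 to 4, the largest gap between periods is 2, and the whole gap lies in days 8-12.

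**Step 3: distribution of the gap (assumption: independent, uniform start weekdays).** Of the 7 x 7 = 49 pairs, 21 have no gap, 20 differ by 1 and 8 differ by 2.

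- Unequal: 28/49 = 57%. Differ by 2: 8/49 = 16%.
- Variance = (20 x 1 + 8 x 4)/49 = 1.06; SD = 1.03 days.
- If challenges fall only on Monday to Friday (also an assumption), the Sat/Sun figures are 56%, 24% and SD 1.13; the Fri/Sat figures are 64%, 16% and SD 1.06.

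**Step 4: effect on the treatment contrast.** Let r be the weekend effect divided by the SD of a subject's period-mean difference. The documents give neither quantity, so r = 0.5 to 2 is an assumed range. Variance inflation is (1.03 r/12)² for the 12-day mean and (1.03 r/5)² for days 8-12.

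| r | 12-day mean | Days 8-12 |
|---|---|---|
| 0.5 | 0.2% | 1.1% |
| 1 | 0.7% | 4.2% |
| 2 | 2.9% | 17% |

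On a base of 28 subjects this equals about 0.05, 0.2 and 0.8 subjects for the 12-day mean, and 0.3, 1.2 and 4.8 for days 8-12. Counting Friday to Sunday as weekend and restricting challenges to weekdays raises the r = 2 figure for the 12-day mean to 4.4%.

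**Step 5: a second set of assumptions, in drinks.** Take Monday-Friday challenges and Fri/Sat as weekend, so the 12-day counts are 4, 4, 3, 2, 3 and the variance of the gap is 2 x 0.56 = 1.12. Assume a weekend effect D of 2 to 4 drinks, a day-level SD of 3 to 4 and a subject-by-period SD of 0.5 to 1.0.

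- Low end: 1.12 x (2/12)² / [2 x (1.0² + 4²/12)] = 0.031/4.67 = 0.7%.
- High end: 1.12 x (4/12)² / [2 x (0.5² + 3²/12)] = 0.124/2.0 = 6.2%.

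The high end pairs the largest weekend effect with the smallest SDs. It widens the standard error by √1.062 - 1 = 3%.

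**Step 6: simulation.** With 28 subjects, 4,000 runs and weekend effects of 0.5 to 1.5 units against a day-level SD of 1.2, the variance ratio without versus with a weekend term was 1.003 to 1.016 for the 12-day mean and 1.01 to 1.09 for days 8-12. There was no material bias.

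**The case against.** The case for leaving the plan alone is reasonable. Randomised order means the weekend gap favours neither treatment in expectation, and unmodelled weekday variation simply stays in the error. Only secondary hypotheses are involved. The documents give no evidence of a weekend pattern in this population, whose members average at least 14 (women) or 21 (men) drinks a week. The scheduling freedom could also lead to same-weekday bookings, since offsets of 21 and 28 days are allowed. All of this stands, and it limits the point to a small gain in precision.

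Some stronger readings are tempting, but the documents do not support them.

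- **That TLFB drinking is modelled with Day and Treatment.** Section 12.1 states the Day factor for daily VAS and sleep only. OCDS is taken on days 7 and 11 (Appendix A), so it is not a daily series either.
- **That the loss is 4-32%.** With the drink assumptions above, a days 8-11 contrast gives 0.4/10 = 4% to 1.6/5 = 32% (Fri/Sat counts 2, 2, 1, 0, 0; variance of the gap 1.6). But section 12.1 specifies no such contrast, and the units are drinks, so the figures do not transfer to VAS or sleep.
- **That all 12 days are ordinary home days.** Day 12 is the laboratory challenge day, with a blood alcohol level of 0.000 required. For a Friday challenge, the only Fri/Sat day in days 8-12 is that laboratory day.
- **That treatment estimates are biased or the primary outcome is weakened.** Neither follows.

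**Conclusion.** The point holds as a minor one. The omission and the possible gap of two weekend days follow directly from sections 9 and 12.1. That study Day cannot absorb the gap follows from staggered start weekdays.

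The size is not fixed by the documents. Across the assumed ranges it runs from close to nothing to about 6% of the variance of the 12-day treatment contrast, with the upper end worked in drinks and not in VAS or sleep units. It is larger for anything that isolates the later days, such as a Day by Treatment interaction. The estimates assume that a weekend effect exists and that the weekdays of the two periods are booked independently; if either fails, the loss shrinks towards zero.

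**What to change.** Prespecify a weekend indicator, or a day-of-week factor, as a fixed effect in the daily VAS model (H5) and the daily sleep model (H6), and define which days count as weekend before unblinding. For sleep, code the term by the night that the entry describes and not by the entry date, since a morning entry refers to the night before. If TLFB is analysed by day, add the same term there and treat day 12 as a laboratory day.

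The cost is 1 degree of freedom for a weekend indicator or 6 for day of week, against up to 28 x 24 = 672 daily entries. No new data should be needed: the weekday can be derived from the dates of the daily smartphone entries. That these are dated is an inference from the daily capture described in section 9. Matching the weekday of the two challenges is optional and not needed once the term is in the model.
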